9. STATISTICAL ANALYSIS

This section presents general information about statistical considerations and concepts and a brief discussion on analysis methodology, as well as some data conventions. Detailed descriptions of the statistical analysis methods and data conventions that will be used in this study will be in a separate document; i.e., the Statistical Analysis Plan (SAP).

9.1. TREATMENT GROUPS

There will be two treatment groups in the study:

- Arm A: Best supportive and/or standard of care in combination with CX-4945 1000 mg BID PO or
- Arm B: Best supportive/standard of care

9.2. DESCRIPTION OF STUDY OUTCOMES (ENDPOINTS)

For description of study outcomes see the Objectives and endpoints in Section 3

9.2.1. Safety Measures:

- Incidence and severity of adverse events (AEs)
- Incidence of serious adverse events (SAEs)
- Incidence of AEs and SAEs leading to discontinuation of study medication.
- Changes in blood chemistry (including electrolyte abnormalities), hematology and coagulation parameter results
- Changes in vital signs including temperature, pulse, respiratory rate, systolic and diastolic blood pressure
- Changes in physical examination results
- Changes in electrocardiogram (ECG) results

9.3. SAMPLE SIZE DETERMINATION AND RATIONALE

A total of 40 subjects will be randomized 1:1 in this study. The sample size is based on clinical judgment. No statistical power calculation will be used to establish the sample size for this proof-of-concept study.

9.4. RANDOMIZATION

The randomization will use block size of 2 or 4 with a 1:1 ratio of CX-4945 in addition to SoC/supportive care group and SoC/supportive care alone group to ensure balanced distribution of subjects. An individual (pharmacy staff), independent of the clinical trial team, will develop the randomization schedules. Subjects who have provided written informed consent and have met all

CONFIDENTIAL Page 49 of 66

the inclusion criteria and none of the exclusion criteria will be randomized to one of the treatment groups.

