4. STUDY DESIGN

4.1. OVERALL DESIGN

This is a phase II multi-center, randomized, open-label, 2 arm parallel-group controlled interventional prospective study of CX-4945 in patients with severe COVID-19. Up to approximately 40 patients will be enrolled into this study. A screening evaluation will occur within 7 days prior to Day 1. All qualified patients will be randomized at Day 1 in a ratio of 1:1 to one of the following two treatment arms:

- Arm A: SOC*/ best supportive care** in combination with CX-4945 1000 mg BID PO or
- Arm B: SOC*/ best supportive care** alone
- * The standard of care (SOC) is not pre-specified, may vary among patients, and may include agents with anti-viral activity, such as remdesivir, among others. Investigator discretion is to be applied for any established SOC. Active concomitant treatment with other investigational antivirals or immunomodulators are not permitted
- ** Best supportive care is defined as intensive care therapy according to current guidelines, evidence, and best practice, including but not limited to lung protective ventilation, thrombosis prophylaxis, renal replacement therapy when indicated, and access to advanced therapies including extracorporeal membrane oxygenation.

The total duration of the treatment will be 14 days. Patients will be followed up at 28, 45 and 60 days from the start of the treatment. The total duration for each patient in the study (including the screening) will be up to 67 days. For details on randomization see Randomization in **Section 6.1.2.**

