6.1.2. Randomization

Randomized treatment assignments for the subjects will be done after confirmation of subject's eligibility, and prior to any other Day 1 study assessments. Subjects will be allocated randomly into Arm A and Arm B in a 1:1 ratio.

Arm SOC/ Daily dose of Dose AM Dose PM Dose No. of **SUPPORTIVE** CX-4945 administration capsules/day (mg) (mg) **CARE** (mg) b.i.d. (mg) 1000 1000 Assigned by the 2000 1000 10 A investigator 0 0 0 0 0 В Assigned by the investigator

Table 2. Method of Assignment to Treatment

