9.5. BLINDING

This is an open label study.

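### Blocks of 2 or 4 in an open-label trial let an enroller who sees the list's earlier assignments guess the next arm about 71–75% of the time; separately, intended SOC need not be recorded before allocation

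*Combined protocol and SAP*

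**What the plan says.** - **Allocation.** Section 9.4: "The randomization will use block size of 2 or 4 with a 1:1 ratio of CX-4945". It does not say whether one size is used throughout or the two are mixed at random. Section 9.3: "A total of 40 subjects will be randomized 1:1 in this study".
- **Masking.** Section 9.5: "This is an open label study".
- **Safeguards.** Section 9.4: "An individual (pharmacy staff), independent of the clinical trial team, will develop the randomization schedules". Section 6.1.2 adds that assignment "will be done after confirmation of subject's eligibility, and prior to any other Day 1 study assessments".
- **Who decides entry.** The investigator makes the initial eligibility evaluation (section 1.3, footnote 2). Day 1 may fall up to 7 days after screening (section 1.3), and a screen failure may be re-screened under a new number (section 5.2).
- **Background treatment.** SOC is not fixed in advance and may include remdesivir. Section 4.1: "Investigator discretion is to be applied for any established SOC". Table 2 in section 6.1.2 likewise leaves SOC in both arms to the investigator.
- **Not described.** The protocol does not say how an assignment stays concealed until release, or whether the two sites named in the synopsis share one list. It does not require the planned SOC to be written down before allocation.

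**The concern.** Two separate routes to bias are open.

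**Selection.** With small blocks of known size, earlier assignments carry information about the next one. In an open-label trial the people treating the patients see those assignments. An enroller who expects a particular arm can, knowingly or not, bring a patient forward, hold one back within the screening window, or not approach one. Keeping the list in the pharmacy does not prevent this, because the inference uses the pattern and not the list. Confirming eligibility before assignment does not prevent it either, because the guess acts on the decision that comes before.

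**Background treatment.** Once the arm is known, SOC can be chosen differently in the two arms. This follows from open-label care with discretionary SOC and would occur whatever the block size.

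Both routes bear on the between-arm secondary comparisons in section 3: recovery, RT-PCR conversion, inflammatory markers and clinical benefit. With 20 per arm, each patient is 1/20 = 5% of an arm.

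**Working it through.** **Inputs.** N = 40, 1:1 (section 9.3); block size 2 or 4 (section 9.4); two sites (synopsis). The plan has no predictability or power figure to reproduce; section 9.3 says "No statistical power calculation will be used to establish the sample size for this proof-of-concept study". As a consistency check, 40/2 = 20 and 40/4 = 10 complete blocks, so either fixed size gives 20:20.

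**Assumptions.** The enroller knows the possible sizes, sees every earlier assignment on the list (relaxed in step 4), and guesses the arm that is behind, or tosses a coin when the arms are level. Mixed sizes are equally likely.

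**1. Fixed blocks of 2.** The first position is a coin toss and the second is certain.
- Guessed: (1/2 + 1)/2 = 0.75.
- Certain: 1/2.

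**2. Fixed blocks of 4.** Six balanced orders. The guess is right with probability 1/2 at position 1 and 2/3 at position 2. At position 3 the first two are alike with probability 1/3 (then certain) and otherwise level, giving 1/3 + (2/3)(1/2) = 2/3. Position 4 is certain.
- Guessed: (1/2 + 2/3 + 2/3 + 1)/4 = 2.833/4 = 0.708.
- Certain: (1/3 + 1)/4 = 0.333.

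**3. Random mix of 2 and 4.** Mean block length is 3.
- Guessed: correct guesses per block are (1.5 + 2.833)/2 = 2.167, and 2.167/3 = 0.722.
- Certain: only when a lead of 2 opens, which reveals a block of 4 and fixes its last two places. That is (1/2)(1/3)(2) = 1/3 per block, or 1/9 = 11.1%.
- These are long-run values. Simulating 4,000 lists of 40, with an observer who updates the probabilities, gives 72.0% and 10.8%.

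**4. One list shared by two sites, each seeing only its own patients.** In 20,000 simulated lists, guessing accuracy is about 55% at an even split, 58–59% for a site with 75% of patients, and 62–63% for a site with 90%. If each site has its own list, the figures in steps 1 to 3 apply at each site.

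**5. Random mix of 4, 6 and 8.** Correct guesses per block are 2.833, 6 × 0.6833 = 4.10 and 8 × 0.6661 = 5.33. The sum is 12.26 over 18 places, or 0.681 in the long run. Simulated lists of 40 give 67.6% guessed and 2.3% certain.

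The last column is the expected number of correct guesses above chance, 40 × (accuracy − 0.5).

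| Scheme | Certain | Guessed | Above chance, of 40 |
|---|---|---|---|
| Fixed 2 | 50% (20 of 40) | 75.0% | 10.0 |
| Fixed 4 | 33% (13.3 of 40) | 70.8% | 8.3 |
| Mix 2/4 | 10.8% (4.3 of 40) | 72.0% | 8.8 |
| Mix 4/6/8 | 2.3% (0.9 of 40) | 67.6% | 7.0 |
| Shared list, even split, own site only | not computed | about 55% | about 2 |

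The share predictable with probability of at least 2/3 is 55% under the 2/4 mix and 60% under 4/6/8. On that measure larger blocks bring no gain; their benefit is that they remove most certain assignments.

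**6. SOC records set against the time of allocation.** Current therapies are recorded at screening (section 1.3, footnote 3), up to 7 days before Day 1. On Day 1, randomization precedes the review of medication changes (section 8.1.2). The last SOC record sure to predate knowledge of the arm is therefore the screening one, and it shows current treatment, not intended treatment.

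**The case against.** - **Visibility is assumed.** There are two sites and the list structure is unstated. With a shared list and no sight of the other site, guessing is only modestly better than chance. This stands, and the claim has to be conditional. The plural for schedules in section 9.4 does not settle the question.
- **Safeguards exist.** Independent staff make the schedule, eligibility is confirmed first, and a screening log records reasons for ineligibility (section 13.1). Most entry criteria are measured thresholds, so there is limited room to declare a patient ineligible at will. This narrows the opening but does not close it, because timing and the decision to approach a patient remain free.
- **SOC is already documented.** Concomitant medication is collected through Day 28 and summarized by arm (sections 1.3, 9.8.2 and 9.8.3), other investigational antivirals and immunomodulators are barred, and covariates are left to the SAP (section 9.7.2). These records would show a difference between arms. They do not give an intended-SOC covariate fixed before allocation.
- **The remedy for blocks is modest.** This stands: guessing falls only from 71–75% to about 68%.
- **The trial is exploratory.** The primary endpoint is adverse events and section 9.8.4 plans no inferential statistics. That limits the consequence. Even so, section 9.8.4.1 names ANCOVA, logistic or proportional-odds and Cox models, and selection biases a descriptive contrast too.

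**Conclusion.** The point holds conditionally, as an improvement that should be made at low cost. If the enroller sees all earlier assignments on the list, about 71–75% of assignments can be guessed, and 50%, 33% or about 11% are certain under fixed 2, fixed 4 or a random mix. If the sites share a list blindly, guessing is about 55–63%. The mixed-block figures rest on equally likely sizes known to the observer.

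A reader might go further and infer that the next assignment is largely foreseeable in this trial. The documents do not support that without the condition, because they state neither the list structure by site nor whether sizes are mixed. A reader might also treat arm-dependent SOC as a result of the small blocks; it is a separate open-label problem. Nor do the documents allow the bias to be sized. The counts above measure opportunity, not steering, and the planned medication summaries would give partial evidence of any SOC difference.

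**What to change.** 1. **Section 9.4.** For patients not yet randomized, drop block size 2, use randomly varying larger blocks (for example 4, 6 and 8), and keep the sizes out of site-facing documents. State how an assignment is concealed until release and whether each site has its own list.
2. **Section 6.1.2.** Before the pharmacy releases an assignment, have the investigator file confirmed eligibility and the current or intended SOC (remdesivir yes/no, dexamethasone yes/no, other). Use that record as the baseline SOC covariate, and report by arm any SOC started after allocation. Investigators keep full discretion over SOC. This step matters more than the first, because it deals with the problem that block size cannot touch.

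**Cost.** A new list, one short form per patient, and a possible arm-size difference of up to 4 patients per list if enrolment stops halfway through a block of 8. With one list per site that could reach 2 × 4 = 8 of 40.

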9.5. BLINDING

This is an open label study.

9.6. INTERIM ANALYSIS

No Interim Analysis (IA) is planned for this study.

9.7. GENERAL STATISTICAL CONSIDERATIONS

All collected study data will be presented in subject data listings. Descriptive statistics (n, mean, standard deviation, median, minimum and maximum) will be presented by treatment group for continuous variables. Frequencies and percentages will be presented by treatment group for categorical variables.

9.7.1. Analysis Populations

9.7.1.1. Intent-to-Treat Population

The Intent-to-Treat (ITT) population is defined as all randomized subjects. This population will be used as the primary analysis population for analysis of the primary and secondary efficacy endpoints.

9.7.1.2. Per Protocol Population

The Per Protocol (PP) population is defined as the set of subjects who meet the ITT Population requirements and are not associated with any major protocol violations. This population will be identified before the database lock. This population will be used as the supportive analysis population for analysis of the primary and secondary efficacy endpoints.

9.7.1.3. Safety Population

The Safety population is defined as any subject receiving at least one dose of CX-4945 or standard of care treatment after randomization. This population will be used for the analysis of safety parameters.

9.7.2. Covariates

For efficacy analyses important prognostic factors that need adjustment will be specified in the Statistical Analysis Plan (SAP) for the study

9.7.3. Missing Data

CONFIDENTIAL Page 50 of 66

The method for handling missing data will be included in the statistical analysis plan. Every effort will be made to obtain required data at each scheduled evaluation from all subjects who have been randomized in the study to minimize missing data. However, in the event when there is missing data the following imputation methods will be used.

For activity/efficacy evaluations, multiple imputation methods will be used to handle missing data and will be detailed in the Statistical analysis Plan (SAP). This imputation method is a robust method to impute potential missing measurements.

9.8. ANALYSIS METHODS

A statistical analysis plan (SAP) will be developed and approved before the database is locked. The SAP will present the detailed statistical methodology to be used in analyzing the data from this trial.

9.8.1. Subject Disposition

The disposition of all subjects who signed an ICF will be provided. The number of subjects screened, screen failed, received at least one treatment, completed, and discontinued during the study, as well as the reasons for all discontinuations will be summarized by treatment group. Disposition and reason for study discontinuation will also be provided as a by-subject listing.

9.8.2. Demographic and Baseline Characteristics

Demographics and baseline characteristics including medical history, prior and concomitant medications/therapies will be summarized by treatment group using appropriate descriptive statistics.

9.8.3. Concomitant Medications/Therapies

Concomitant medications/therapies will be summarized separately for the Safety population. It will be coded to matching Anatomic Therapeutic Classification codes using the most recent version of the WHO Drug Dictionary. Descriptive summaries by treatment group will be prepared using the coded term.

9.8.4. Study Outcome Assessment

For continuous variables data will be summarized by treatment using n, mean, SD, minimum and maximum values. For categorical variables data will be summarized by treatment using frequency and percentage. No inferential statistics are planned. The Safety Population will be used for the analysis of safety outcomes.

9.8.4.1. Efficacy Analysis

Analysis of the efficacy endpoints will be summarized according to the variable type and will be detailed in the SAP:

CONFIDENTIAL Page 51 of 66

• Continuous data:

- o If the normality assumption is met, Analysis of Covariance (ANCOVA) would be used.
- If the normality assumption is not met, a non-parametric method or a rank –
 ANCOVA analysis i.e., an ANCOVA analysis on rank-transformed data will be used.
- Categorical data summaries will be based on logistic regression or proportional odds model will be used.
- Time-dependent data: Cox proportional hazards model will be used to analyze time dependent data and Kaplan-Meier methods will be used to depict the time to event data.

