mmHg). All these improvements must be sustained for at least 48 hours. Percentage of Participants at Each Clinical Status at Day 14 and Day 28 assessed by using the ordinal NIAID 8- point Clinical Progression Outcomes scale: 1) Death; 2) Hospitalized, on invasive mechanical ventilation extracorporeal membrane oxygenation *(ECMO)*; 3) Hospitalized, on non-invasive ventilation or high flow oxygen devices; 4) Hospitalized, requiring supplemental oxygen; 5) Hospitalized, not requiring supplemental oxygen - requiring ongoing medical care (COVID-19 related or otherwise); 6) Hospitalized, not requiring supplemental oxygen - no longer requires ongoing medical care; 7) Not hospitalized, limitation on activities and/or requiring home oxygen; 8) Not hospitalized, no limitations on activities To evaluate preliminary Difference in proportions of patients with evidence of anti-viral conversion of positive RT-PCR to negative RTactivity of CX-4945 as PCR as assessed at Day 1, Day 8, Day 14 and Day compared to the control 28. arm. Changes in chest imaging from Screening to Day 5 or 14 (if applicable) as defined by: Number of quadrants/ pulmonary lobes affected Change in number and/or size of COVID-19 pulmonary lesions (ground-glass opacity, consolidation, mix pattern) assessed by chest CT/X-ray

CONFIDENTIAL Page 11 of 66

[figure not shown]
	To evaluate the Clinical Benefit of Silmitasertib (CX-4945) relative to the control arm in patients with Severe COVID-19.	 Days of hospitalization from randomization through Day 28. Days of supplemental oxygen (if applicable) from randomization through Day 28. All-cause mortality status - the number of deaths occurred in each treatment group from randomization through Day 60. Days of non-invasive ventilation/high flow oxygen (if applicable) from randomization through Day 28. Days of invasive mechanical ventilation/ECMO (if applicable) from randomization through Day 28. Number of patients returned to room air after randomization through Day 14 or Day 28. Change in pulse oxygen saturation (SpO2) from randomization to Day 4, 8, 11, 14 and 28. Number of documented venous thromboembolism (VTE), arterial thrombosis (stroke, myocardial infarction, other) and microthrombosis events from randomization through Day 28. Changes in EQ-D5-5L (used as an indicator of symptom improvement) from randomization to Day 8, 14 and 28.

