3. OBJECTIVES AND ENDPOINTS

Primary Objective	Primary Endpoint
To assess safety and tolerability of CX-4945 administered orally twice daily to patients with severe COVID-19	• Adverse Events experienced by patients from randomization to Day 60 (including vital signs, physical findings, clinical laboratory, and ECG results) as characterized by type, frequency, severity (as graded by Common Terminology Criteria for Adverse Events (CTCAE version 5.0), timing, seriousness, and relationship to study therapy.
Secondary Objectives	Secondary Endpoints
• To compare time to clinical recovery in the CX-4945 treatment group evaluated from randomization through Day 28 as compared to the control arm.	• Number of days from randomization to discharge, or alleviation of cough (defined as mild or absent in a patient reported scale of 0=absent, 1=mild, 2=moderate, and 3=severe). Improvement must be sustained for at least 48 hours.
	• Number of days from randomization to normalization of fever (defined as <36.6°C from axillary site, or < 37.2°C from oral site or < 37.8°C from rectal or tympanic site), normalization of respiratory rate (< 24 bpm while breathing room air), resolution of hypoxia (defined as SpO2 ≥ 93% in room air or P/F ≥ 300 mmHg). All these improvements must be sustained for at least 48 hours.
	 Number of days from randomization to the first day on which the subject satisfies one of the following three categories from the ordinal NIAID 8-point Clinical Progression Outcomes scale collected daily from randomization through Day 28:
	Hospitalized, not requiring supplemental oxygen - no longer requires ongoing medical care;
	 Not hospitalized, limitation on activities and/or requiring home oxygen;
	Not hospitalized, no limitations on activities.
To compare changes in clinical status of patients enrolled to CX-4945 treatment arm as	Difference in percentage of subjects with clinical recovery compared at Day 14 and Day 28. Clinical recovery is defined as:

CONFIDENTIAL Page 22 of 66

s. ty	ite, or < 37.2°C from oral site or < 37.8°C from rectal or ympanic site), normalization of respiratory rate (< 24 bpm
a	while breathing room air), resolution of hypoxia (defined as $SpO2 \ge 93\%$ in room air or $P/F \ge 300$ mmHg). All these mprovements must be sustained for at least 48 hours.
Day	centage of participants at each clinical status at Day 14 and 28 assessed by using the ordinal NIAID 8- point Clinical gression Outcomes scale:
1) L	Death;

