	Hospitalized, on invasive mechanical ventilation or acorporeal membrane oxygenation (ECMO);
· · · · · · · · · · · · · · · · · · ·	Hospitalized, on non-invasive ventilation or high flow gen devices;
4) H	Hospitalized, requiring supplemental oxygen;
	Hospitalized, not requiring supplemental oxygen - requiring oing medical care (COVID-19 related or otherwise);
· ·	Hospitalized, not requiring supplemental oxygen - no longer uires ongoing medical care;
	Not hospitalized, limitation on activities and/or requiring ne oxygen;
8) N	ot hospitalized, no limitations on activities
evidence of anti-viral activity of CX-4945 as compared to the Day	Gerence in proportions of patients with conversion of tive RT-PCR to negative RT-PCR as assessed at Day 1, 8, Day 14 and Day 28
	inges in chest imaging from Screening (Day 0)to Day 5 or 14 (if applicable) as defined by:
0]	Number of quadrants/ pulmonary lobes affected

CONFIDENTIAL Page 23 of 66

	 Change in number and/or size of COVID-19 pulmonary lesions (ground-glass opacity, consolidation, mix pattern) assessed by chest CT/X-ray
To evaluate the Clinical Benefit of Silmitasertib (CX-4945) relative to the control arm in patients with Severe COVID-19.	 Days of hospitalization from randomization through Day 28. Days of supplemental oxygen (if applicable) from randomization through Day 28. All-cause mortality status: the number of deaths occurred in each treatment group from randomization through Day 60. Days of non-invasive ventilation/high flow oxygen (if applicable) from randomization through Day 28. Days of invasive mechanical ventilation/ECMO (if applicable) from randomization through Day 28. Number of patients returned to room air after randomization through Day 14 or Day 28. Change in pulse oxygen saturation (SpO2) from randomization to Day 4, 8, 11, 14 and 28. Number of documented venous thromboembolism (VTE), arterial thrombosis (stroke, myocardial infarction, other) and microthrombosis events from randomization through Day 28. Changes in EQ-D5-5L (used as an indicator of symptom improvement) from randomization to Day 8, 14 and 28.
To evaluate changes in inflammatory markers	 Changes in plasma IL-6 level from randomization to Day 4, 8, 11, and 14 Changes in CRP, LDH, CPK, ferritin, D-dimer from randomization to Day 4, 8, 11, and 14

CONFIDENTIAL Page 24 of 66

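### Recovery and RT-PCR conversion are defined as differences in percentages, but the only models named give odds ratios; no interval for the difference and no method for zero cells is planned

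*Combined protocol and SAP*

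**What the plan says.** Section 3 (Objectives and Endpoints) defines the recovery endpoint as "Difference in percentage of subjects with clinical recovery compared at Day 14 and Day 28". The RT-PCR endpoint is worded on the same scale: the synopsis opens it with "Difference in proportions of patients with" conversion from positive to negative, assessed at Days 1, 8, 14 and 28.

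Two other secondary endpoints in Section 3 are defined as counts. For mortality it is "the number of deaths occurred in each treatment group from randomization through Day 60". For thrombosis it is "Number of documented venous thromboembolism (VTE), arterial thrombosis (stroke, myocardial infarction, other) and microthrombosis events from randomization through Day 28".

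Section 9.8.4.1 assigns methods by variable type. For categorical efficacy data the whole instruction is: "Categorical data summaries will be based on logistic regression or proportional odds model will be used". It mentions no risk difference, no exact or penalised method, and no step that turns model output into a difference. Details are left to a separate SAP, which is not among the documents.

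Four other provisions bear on this:

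- Sections 9.7 and 9.8.4 present categorical data as frequencies and percentages by arm. Section 9.8.4 adds that inferential statistics are not planned.
- Section 9.7.2 leaves the prognostic factors for adjusted efficacy analyses to the SAP.
- Section 9.7.3 plans multiple imputation for missing efficacy data.
- Section 9.3 fixes the size: "A total of 40 subjects will be randomized 1:1 in this study". It adds: "No statistical power calculation will be used to establish the sample size for this proof-of-concept study".

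**The concern.** There are two separate issues, and they concern different endpoints.

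The first is scale. An endpoint defined as a difference in percentages should come with an estimate and an interval on that scale. A logistic model reports an odds ratio, and the same odds ratio corresponds to different risk differences at different control rates. If the SAP follows Section 9.8.4.1 literally, the modelled result for recovery and RT-PCR conversion will not be the quantity the protocol defines. The defined quantity will appear only as two percentages, with nothing to show how imprecise their difference is at 20 patients per arm.

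The second is sparse data. Deaths and thrombotic events may be few. If they are analysed as yes/no outcomes by ordinary logistic regression, an arm with no events leaves the treatment odds ratio infinite, or undefined if both arms have none. Adjusting for prognostic factors cannot cure this and can make separation more likely.

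What is at stake is how the secondary results are read. Section 2.3 says that the secondary objectives supply the initial assessment of possible clinical benefit.

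**Working it through.** **Inputs.** From Section 9.3: 40 patients at 1:1, so 20 per arm. The documents give no event rates and no power calculation, so there is no planned figure to reproduce. All rates below are assumptions.

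**Step 1: do the scales differ materially?** Odds ratio = [b/(1−b)] / [a/(1−a)].

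- 50% v 70%: difference 20 points; odds ratio (0.70/0.30)/(0.50/0.50) = 2.33.
- 70% v 85%: difference 15 points; odds ratio (0.85/0.15)/(0.70/0.30) = 2.43.
- 5% v 15%: difference 10 points; odds ratio (0.15/0.85)/(0.05/0.95) = 3.35.

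As the difference falls from 20 to 10 points, the odds ratio rises from 2.33 to 3.35. One cannot stand in for the other.

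**Step 2: how often would a sparse yes/no outcome have no finite estimate?** At low rates this is the chance that at least one arm of 20 has zero events: P = 1 − [1 − (1−p)^20]² for a common rate p.

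| Rate in both arms | (1−p)^20 | P |
|---|---|---|
| 5% | 0.358 | 59% |
| 10% | 0.122 | 23% |
| 15% | 0.039 | 8% |
| 20% | 0.012 | 2% |

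With unequal rates, P = 1 − [1 − (1−pA)^20][1 − (1−pB)^20]. This gives 44% for 5% v 10% and 13% for 10% v 20%.

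An arm in which every patient has the outcome causes the same failure, so the figures mirror near 100%: 23% at 90% in both arms and 59% at 95%. At 30% to 70% in both arms the chance is at most 0.2%.

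**Step 3: what happens in a concrete case?** A standard logistic fit of 0/20 v 3/20 did not converge. It stopped at a log odds ratio of about 30 with a standard error of about 1.7 million.

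**Step 4: do the alternatives work?**

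- 3/20 v 0/20: risk difference +15 points, Newcombe 95% CI −3.8 to +36.0. The Firth odds ratio, which in a 2×2 table amounts to adding 0.5 to each cell, is (3.5/17.5)/(0.5/20.5) = 8.2.
- 14/20 v 10/20: risk difference +20 points, Newcombe 95% CI −9.7 to +45.3.

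The second interval is 55 points wide. Two bare percentages would not show that.

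**The case against.** The strongest reply is that the plan already delivers the stated quantity. Counts and percentages per arm are reported for every categorical variable, subtraction gives the difference even with a zero cell, and Section 9.8.4 disclaims inference. This largely stands for the point estimate. A reader might infer that following the plan leaves no usable result for these endpoints; the documents do not support that. What is missing is an interval. The disclaimer does not settle the matter either, because Section 9.8.4.1 goes on to name ANCOVA, logistic, proportional odds and Cox models. The two sections need reconciling.

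A second reply is that the sparse-data figures do not belong to the endpoints defined as differences. This also stands. A reader might infer that logistic regression will often fail for recovery or RT-PCR conversion, but nothing in the documents shows these to be rare. Failure would need rates close to 0% or 100%, which is conceivable for conversion at Day 1 or recovery at Day 28 but is not established. Deaths and thromboses are defined as counts. A patient can have several thrombotic events, and Section 9.8.4.1 does not expressly send either endpoint to logistic regression. Step 2 therefore applies only if they are analysed as yes/no outcomes there.

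A third reply is that details are deferred to the SAP, and that Firth's method and marginal standardisation both belong to the logistic family. They are not excluded, but they are not planned either. The protocol has already named the model, so a SAP that simply follows it inherits the gap.

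**Conclusion.** The point holds in two limited parts.

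First, for clinical recovery and RT-PCR conversion, the named models estimate an odds ratio while the endpoint is a difference. The raw difference is available from the reported percentages, but no interval for it is planned. This follows from the text alone and needs no assumed rates.

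Second, if death or any thrombotic event is handled as a yes/no outcome by ordinary logistic regression, the chance of no finite treatment estimate runs from 59% at 5% incidence in both arms to 2% at 20%. This is conditional on that handling and on assumed rates. It would be wrong to say without those conditions that the analysis often fails.

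The priority is minor. These are secondary endpoints of an exploratory, unpowered trial whose primary endpoint is safety, and the documents tie no decision rule to the odds ratio.

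**What to change.** In the SAP, before database lock:

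1. Reconcile the disclaimer of inference in Section 9.8.4 with the models in Section 9.8.4.1, and label any intervals as exploratory estimation.
2. For each binary endpoint, report the risk difference with a Miettinen-Nurminen or Newcombe 95% interval beside the counts and percentages.
3. Where covariate adjustment (Section 9.7.2) or multiple imputation (Section 9.7.3) applies to common outcomes, obtain the risk difference by marginal standardisation from the logistic model and combine it across imputations by Rubin's rules.
4. If an odds ratio is wanted for a sparse outcome, use Firth-penalised logistic regression.
5. Analyse thrombosis as patients with at least one event, alongside the event count.
6. Keep the proportional odds model for the 8-point scale.

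The cost is SAP wording and standard software, with no extra patients, visits or data. The drawback is that unadjusted differences are slightly less efficient than adjusted ones for common outcomes. The size of that loss cannot be given from the documents; item 3 avoids it where adjustment is used.
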